### **11.3.5. Safety Analysis**

Safety evaluations will be based on the incidence, severity, and type of AEs and clinically significant changes in the subject's physical examination findings, vital signs, and clinical laboratory results. Safety variables will be tabulated and presented for all subjects in the Safety Population. Data will be summarized by treatment and time. Exposure to study drug and reasons for discontinuation of study drug will be tabulated.

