#### 3.1.2 Safety Analysis Set Extension (SAFe)

The SAFe population includes all patients enrolled in ADOREXT who have received at least one dose of the investigational drug during the extension study, irrespective of satisfying other criteria. This population will be used for the analysis of safety and tolerability, and statistical analysis will be done “as treated”. Although all patients will be treated with FAB122 in ADOREXT, data will be presented also using the randomization groups of ADORE study.

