### 5 STATISTICAL ANALYSIS

#### 5.1 General considerations

Appropriate rounding will be performed for the summary statistics: arithmetic mean, median, SD (standard deviation) and confidence limits will be presented with one more decimal than the original data; minimum and maximum values will be presented with the same precision as the original data. In frequency tables, percentages will be presented with 1 decimal. P-values will be presented with 3 decimals, and those smaller than 0.001 will be replaced by <0.001.

Descriptive statistics presented in general summary tables will be the number of non-missing observations (n), mean, SD, minimum, median and maximum for quantitative data. For categorical data, frequency counts and percentages will be determined. The denominator when calculating percentages will be the number of patients in the applicable analysis population. Descriptive statistics will be displayed for all visits that a measurement is collected on, even if the endpoint is only referring to limited visits for the analysis.

Baseline is defined as the last value measured prior to first study treatment administration in ADOREXT study, unless otherwise specified. Typically, baseline data are collected at Visit 6 or 8 of the ADORE study. In case this value is missing for a specific patient in ADOREXT CRF data, but an earlier measurement is collected in ADORE study data, this value will be used as baseline instead. Unscheduled measurements are excluded as baseline value.

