#### **5.4.3 Disposition**

To present disposition, summaries will be provided for all randomized, enrolled in extension, treated in extension, and completed extensions along with reasons for early discontinuation. Completion status will be derived from CRF form “Study Completion”. Additionally, the number/percentage of patients in the mITT and SAFe will be presented. The patient disposition will be presented per treatment group and overall.

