### **5.6.1 Adverse events**

A treatment emergent adverse event (TEAE) is defined as an adverse event that appears at or after first dosing of extension. In case of (partially) missing start/stop dates, refer to Section [5.2](#).

An AE overview table will be created displaying the number of patients (and percentage) experiencing a treatment-emergent adverse event (TEAE) and the number of TEAEs for: any TEAE, any mild/moderate/severe TEAE, any unrelated/related TEAE, any serious AE, any serious TEAE, and any TEAE leading to study treatment discontinuation, any AE leading to death.

All TEAEs and those leading to death will be tabulated. SUSARs will be reported by the pharmacovigilance vendor.

All TEAEs are tabulated by System Organ Class (SOC) and Preferred Terms (PTs) within each SOC according to the MedDRA terminology list. TEAEs will be tabulated using frequency counts (number of patients with at least one event, and number of events) and percentage of patients with the event. Similar tables will be created for TEAEs leading to premature treatment discontinuation and Serious TEAEs. These summary tables will be presented by decreasing frequency of occurrence based on SOC and PT.

For summary tables, an AE is considered related if the causality to the study medication is classified as either ‘Probably Related’ or ‘Possibly Related’, where a missing relationship is also considered related. Otherwise, it will be considered unrelated for summary tables.

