## **5.7 Scheduled visits, dosing and treatment compliance**

Not applicable / not in the scope of this SAP following early termination of the study.

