## **6 CHANGES FROM PROTOCOL AND OTHER RELEVANT REMARKS**

Due to study early termination, some analysis planned in the protocol will not be performed. This SAP focuses on a subset of analyses related to objectives of safety, overall survival, and

disease progression. In particular, analysis will be performed for the primary endpoint, the overall survival and survival time. The ALSFRS-R score will also be described.

Overall survival and survival time endpoints definition will be updated to align with ADORE study. ALSFRS-R is also added to the secondary endpoints as it will be analyzed without mortality adjustment.

The mITT analysis set was not originally planned in the study protocol and included in the SAP to perform survival analysis combining ADORE and ADOREXT data.

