### 9.3 End-of-text tables and graphs

Following ICH E3 guidelines, all tables and graphs mentioned here will be presented in Section 14 of the CSR, and tables will be prepared in the order and with section number as stated.

Table /graph number	Contents of table/graph
14.1 Demographic Data Summary figures and tables	
14.1.1	Demographics
14.1.2	Baseline Characteristics
14.1.3	ALS-specific history
14.1.4	Disposition
14.2 Efficacy Data Summary Figures and Tables	
14.2.1.1	Survival time: descriptive statistics
14.2.1.2	Survival time: Kaplan-Meier curves
14.2.1.3	Survival time: statistical analysis results (RMST)
14.2.2.1	Overall survival: descriptive statistics
14.2.2.2	Overall survival: Kaplan-Meier curves

14.2.2.3	Overall survival: statistical analysis results (RMST)
14.2.3.1	Descriptive statistics for absolute values and change from baseline ALSFRS-R total score and function domains
14.3 Safety Data Summary figures and tables – 14.3.1 Displays of Adverse Events	
14.3.1.1	Overview adverse events
14.3.1.2	Treatment emergent adverse events by SOC and PT
14.3.1.3	Treatment emergent serious adverse events by SOC and PT
14.3.1.4	Treatment emergent adverse events leading to treatment discontinuation by SOC and PT
14.3 Safety Data Summary figures and tables – 14.3.2 Listings of Deaths, Other Serious and Significant Adverse Events	
14.3.2.1	Deaths
14.3.2.2	TEAEs

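### The protocol promises a table of exposure to study drug; the SAP drops it, so the planned outputs give TEAE percentages with no time on drug behind them

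*SAP*

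**What the plan says.** Protocol 11.3.5, repeated in the synopsis, commits to this: "Exposure to study drug and reasons for discontinuation of study drug will be tabulated". The protocol's primary objective is long-term safety, and its primary endpoint is the nature, frequency and severity of TEAEs.

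The SAP keeps that endpoint. Section 6 says that after early termination "analysis will be performed for the primary endpoint, the overall survival and survival time", with ALSFRS-R also described. Section 5.6.1 sets the metric: "TEAEs will be tabulated using frequency counts (number of patients with at least one event, and number of events) and percentage of patients". Section 5.1 sets the denominator: "The denominator when calculating percentages will be the number of patients in the applicable analysis population". Section 3.1.2 adds that, although everyone receives FAB122 in the extension, "data will be presented also using the randomization groups of ADORE study".

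Section 5.7, which covers scheduled visits, dosing and treatment compliance, reads in full: "Not applicable / not in the scope of this SAP following early termination of the study". Among the AE summaries listed in 9.3 the last is "Treatment emergent adverse events leading to treatment discontinuation by SOC and PT", followed by the displays of deaths and TEAEs. The list has no exposure, duration or patient-years table. Section 9.4 puts listings out of scope.

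**The concern.** A percentage of patients with an event depends on both the event rate and the time over which events could occur. In a study with a fixed, completed treatment period the second is known. Here it is not. The protocol planned about 3 years, the study was stopped early, and patients entered from ADORE Visit 6 or 8 under country-specific protocol versions. Follow-up is therefore truncated and probably uneven.

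Without exposure, a reader who sees a low TEAE percentage cannot judge how far short time on drug accounts for it. The same holds when TEAEs are split by ADORE arm: a difference or similarity between the former placebo and former FAB122 groups cannot be read without knowing whether their time on drug in the extension was alike. Early termination is the SAP's reason for dropping dosing summaries, yet it is also what makes time on drug informative.

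**Working it through.** **Step 1: commitment against plan.** There is no stated figure to reproduce, so the first check is textual.

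| Item | Protocol | SAP |
|---|---|---|
| Exposure to study drug | To be tabulated (synopsis, 11.3.5) | No table in 9.3; dosing out of scope in 5.7; no listings (9.4) |
| Reasons for stopping study drug | To be tabulated (same sentence) | Partly kept: study disposition (5.4.3) and TEAEs leading to treatment discontinuation |
| Named as a change from protocol | – | Not named; section 6 says only that some analyses are dropped |

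**Step 2: does a retained output fill the gap?** Disposition covers patients who "completed extensions along with reasons for early discontinuation", which gives counts and reasons but no durations. The survival analyses (SAP 4.2, 5.5.2.1) run from treatment start in ADORE, so their time axis mixes ADORE time, including placebo time, with extension time, and continues whether or not the patient is on drug. Neither gives time on FAB122 in the extension.

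**Step 3: how much the missing time matters.** Mean exposure is not in the documents, so the times below are assumptions. The model is a constant hazard with equal follow-up *t* (years) and proportion *p* with an event: rate = −ln(1 − *p*)/*t*.

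For *p* = 0.25, −ln(0.75) = 0.2877:

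| Follow-up | Calculation | First events per 100 patient-years |
|---|---|---|
| 3 months | 0.2877/0.25 | 115.1 |
| 6 months | 0.2877/0.5 | 57.5 |
| 12 months | 0.2877/1 | 28.8 |

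**Step 4: a rough scale from document dates.** The country protocol versions named in SAP 1 are dated 24 Jan 2023 to 10 Jul 2023; the SAP is dated 19 Apr 2024. The intervals are 451 days (14.8 months; 451/1095.75 = 41% of 3 years) and 284 days (9.3 months; 284/1095.75 = 26%). These dates do not bound exposure: they are not first-dose dates, earlier versions may have been in use, and the SAP date is not a last-dose date. At those two follow-up times, one rate of 28.8 per 100 patient-years would appear as:

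- 284 days: 1 − exp(−0.2877 × 284/365.25) = 20.0% of patients
- 451 days: 1 − exp(−0.2877 × 451/365.25) = 29.9% of patients

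**Step 5: an event type with no cases.** Take 200 patients, the low end of the anticipated 200–225, and two-sided 95% limits.

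- Upper limit on the percentage: 1 − 0.025^(1/200) = 1.83%, whatever the exposure.
- Upper limit on the rate (exact Poisson, 3.689/patient-years): with mean 3 months, 200 × 0.25 = 50 patient-years, 3.689/50 = 7.4 per 100 patient-years; with mean 12 months, 200 patient-years, 3.689/200 = 1.8 per 100 patient-years.

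The planned table would look the same in both cases, although the second excludes rates four times lower.

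**The case against.** The strongest reply is that this is an open reduction in scope. SAP 5.7 drops dosing by its heading and gives the reason, and sections 2.1, 4 and 6 each say that only a subset of analyses is kept. Section 9.2 also allows in-text tables to be programmed on request. This stands in part: nothing was hidden, and the gap lies in the planned outputs rather than in what could be produced. It does not answer the point, because section 6 neither names exposure nor says why the retained primary endpoint can do without it.

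Second, the protocol promised that exposure would be tabulated, not patient-years, rates or confidence intervals. That is correct. The departure from protocol is the missing exposure table; rates go further than the protocol.

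Third, the illustrations use assumed event proportions and follow-up, and assume equal follow-up where it is probably uneven. That is also correct. They show how sensitive the reading is to time on drug; they do not estimate anything about this trial.

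Fourth, every patient in the extension receives FAB122, so exposure alone cannot establish drug-related risk. True, but it is still needed to describe how frequent events were and how much long-term experience was gained.

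**Conclusion.** The concern holds. A table that the protocol promises twice, and that gives context to the primary endpoint, is missing from the SAP and is not named in its changes from protocol. Retained outputs do not replace it. No planned analysis is invalidated: the TEAE percentages remain correct crude proportions. What is lost is the ability to say how much time on FAB122 they represent, overall or by ADORE arm. Under a constant hazard and equal follow-up, the same 25% covers a fourfold range of rates between 3 and 12 months (115 to 29 per 100 patient-years), and the same zero count in 200 patients covers a fourfold range in the upper rate limit (7.4 to 1.8). The textual finding needs no assumptions; the sizes rest on assumed exposure. This should be corrected before the tables are produced.

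**What to change.** 1. **Exposure table (restores the protocol commitment).** Add to SAP 5.6.1 or 5.7, and to the list in 9.3, a summary of FAB122 duration in the extension and total patient-years for the SAFe set, overall and by ADORE arm. Because patients randomized to FAB122 may bring ADORE treatment time with them, cumulative exposure for that group is a useful extra line. If the table is still left out, name it in section 6 and give the reason.
2. **Rates (an improvement beyond the protocol).** Beside the percentages, report any TEAE, serious TEAEs, TEAEs leading to discontinuation and deaths per 100 patient-years with 95% CIs. Define time at risk to match event collection: from first extension dose to the follow-up or early withdrawal visit (Protocol 9.5), including time off drug if those events are counted, since Protocol 6.5 lets patients stop treatment and stay in the study. State an end to the TEAE window as well: SAP 5.6.1 gives none, and Protocol 9.6.1 accepts related SAEs at any time after stopping.
3. **Optional and separate.** In SAP 5.2, the rule for a missing start date with a partial stop date requires the stop month or year to fall strictly after that of first dosing, while the partial start-date rule also accepts the same month or year. Accepting the same period in both would fit the stated conservative approach.

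The cost is a few tables. First-dose and AE dates are already needed to classify TEAEs. Last-dose and end-of-study dates must be in the data received; because dosing was put out of scope, the transfer agreements in SAP 7 may need extending.

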### **5.6.2 Other safety endpoints and examinations**

Not applicable / not in the scope of this SAP following early termination of the study.

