## 2 STUDY INFORMATION

### 2.1 Study Objective(s)

The primary objective of this study is to evaluate the long-term safety of FAB122 in patients with Amyotrophic Lateral Sclerosis (ALS).

The secondary objectives of this study are as follows:

- To evaluate the effect of treatment with FAB122 on overall survival

- To evaluate the effect of treatment with FAB122 on disease progression in patients with ALS
- To evaluate the effect of treatment with FAB122 on cognitive functioning
- To evaluate the effect of treatment with FAB122 on quality of life (QoL).

Due to study early termination, some analysis planned in the protocol will not be performed (see Section 6). This SAP focuses on a subset of analyses related to objectives of safety, overall survival, and disease progression.

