### 4.1 Primary endpoint

The primary endpoint is the nature, frequency and severity of Treatment Emergent Adverse Events (TEAEs).

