#### 4.3 Safety endpoint(s)

- Parameters derived from vital signs and 12-lead electrocardiogram (ECG)
- Parameters derived from laboratory tests (hematology, biochemistry, urinalysis)
- Proportion of subjects that drop out due to adverse events.

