## 9.4 Listings

Listings are not in the scope of this SAP.

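### SAP 5.6.2 drops every laboratory, ECG, vital-sign and examination summary from a long-term safety study, although SAP 4.3 still lists the first three as safety endpoints

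*SAP*

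**What the plan says.** SAP 2.1 and Protocol 3.1.1 make long-term safety the primary objective. SAP 4.3 lists three safety endpoints:

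- the first covers measurements from vital signs and the ECG;
- the second reads "Parameters derived from laboratory tests (hematology, biochemistry, urinalysis");
- the third is the share of patients who leave because of adverse events.

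Protocol 11.3.5 bases the safety evaluation on adverse events together with "clinically significant changes in the subject's physical examination findings, vital signs, and clinical laboratory results". Its subsections plan the detail: a tabulation of physical-examination abnormalities (11.3.5.1), laboratory values and changes from baseline over time with out-of-range flags (11.3.5.4), ECG intervals including QTcF at each time point (11.3.5.5), and vital signs at each time point (11.3.5.6).

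The whole text of SAP 5.6.2, which covers the other safety endpoints and examinations, is "Not applicable / not in the scope of this SAP following early termination of the study". SAP 6 says in general terms that early termination means some planned analyses will not be done. It names what is kept, not which safety endpoints go. SAP 9.4 states "Listings are not in the scope of this SAP", while SAP 9.3 plans a section 14.3.2, headed as listings, with outputs for deaths and TEAEs.

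**The concern.** The only reason given is early termination. That limits how long patients were followed. It does not make the laboratory, ECG and vital-sign data collected until then inapplicable. From the same visits the SAP keeps the ALSFRS-R total and four subscales (SAP 5.5.2.2), and it plans restricted mean survival time for two survival endpoints (SAP 5.5.2.1). Secondary efficacy description therefore survives in a safety study while the objective safety measurements do not.

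The adverse event tables do not fully replace them. An abnormal result becomes an adverse event only if it meets one of the conditions in Protocol 9.1.1, and several of these turn on the investigator's judgement in an open-label study. Protocol 8.2.2 likewise asks for significant abnormalities to be recorded. A gradual shift in transaminases, creatinine, blood counts or QTcF that nobody called significant in any one patient would appear nowhere. Nor could the report say how many dosed patients met the numeric laboratory criteria that Protocol 6.5 sets for stopping treatment.

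**Working it through.** The plan states no figure on this point, and no sample-size or power calculation bears on it. The check sets each planned safety item against its schedule and its output.

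| Item | In SAP 4.3? | Analysis planned in the protocol | Schedule (Protocol Table 1, after baseline) | Output in SAP 9.3 |
|---|---|---|---|---|
| Laboratory tests | Yes | 11.3.5.4 | Every 3 months | None |
| Vital signs | Yes | 11.3.5.6 | Every 3 months | None |
| 12-lead ECG | Yes (with vital signs) | 11.3.5.5 | Every 6 months | None |
| Physical examination | No | 11.3.5.1 | Every 6 months | None |
| Neurological examination | No | No separate table | Every 6 months | None |
| Drop-out due to adverse events | Yes | 11.3.3, 11.3.5 | Continuous | 14.3.1.4 and 14.1.4, in substance |

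**Endpoints.** SAP 4.3 has three bullets. Vital signs with ECG is one, laboratory tests another, and neither has an analysis: 2 of 3. The third is covered in substance by the table of TEAEs leading to treatment discontinuation and by the reasons for discontinuation in the disposition table.

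**Outputs.** SAP 9.3 plans six safety outputs: 14.3.1.1 to 14.3.1.4 (four), 14.3.2.1 and 14.3.2.2 (two). Those showing laboratory, ECG, vital-sign or examination data: 0 of 6.

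**Would the Protocol 6.5 criteria surface anyway?** Protocol 6.5 gives numeric criteria for ALT/AST (alone and with bilirubin), creatinine clearance, platelets and neutrophils. A patient who meets one stops treatment but should stay in the study. The Protocol 9.1.1 condition on results that lead to study withdrawal therefore does not capture that patient automatically. Many such patients should appear as adverse events or discontinuations by another route, but no planned output would show whether all of them did.

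**Can the counts be made?** Mostly. Protocol Table 2 lists ALT, AST, direct and total bilirubin, platelets and neutrophils. It lists creatinine and eGFR but not creatinine clearance, so the renal count needs a stated derivation. Some 6.5 criteria also require symptoms, persistence or investigator judgement, and for those laboratory data alone give only the numeric part.

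**Illustration only.** If all of the anticipated 200 to 225 patients were dosed and evaluable, and none met a given criterion, the one-sided upper 95% limit would be about 3/n: 3/200 = 1.5% and 3/225 = 1.3%. The number dosed is not given, so this shows the kind of statement the tables would allow. It does not measure an error in the plan.

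**The case against.** The strongest reply is that the reduction is deliberate and disclosed. SAP 4 introduces its endpoint lists by saying that some planned analyses will not be done and naming what the SAP focuses on. SAP 4.2 in the same way lists secondary endpoints that are not analysed, and the heading of 5.6.2 says what it covers. Listing endpoints in 4.3 without analysing them is therefore not a hidden contradiction. That stands. What remains is that SAP 6, where SAP 4 sends the reader, does not itemise the dropped safety endpoints.

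Second, the primary endpoint is untouched. SAP 4.1 reads "The primary endpoint is the nature, frequency and severity of Treatment Emergent Adverse Events (TEAEs"), and SAP 5.6.1 analyses these by severity, relatedness, seriousness, discontinuation, and system organ class and preferred term. A reader might infer that the primary analysis has been abandoned; it has not.

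Third, a reader might infer that safety now rests on investigator-reported adverse events alone. The documents do not support that. All-cause death is analysed as overall survival with ADORE and ADOREXT combined, deaths are presented, and disposition gives reasons for discontinuation. Protocol 9.1.1 also offers six alternative conditions, not only clinical significance, by which an abnormal result becomes an adverse event. Patients meeting the 6.5 criteria are among those most likely to appear in the discontinuation outputs.

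Fourth, it is tempting to say that all listings are removed. SAP 9.4 says so, but 9.3 places deaths and TEAEs under a listings heading. The accurate finding is that the two sections disagree.

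Fifth, the protocol did not plan shift tables or threshold counts. It planned by-visit summaries and flagged listings. Those two items in the fix are additions and should be judged on their merit.

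**Conclusion.** The point holds in this form: two of the three safety endpoints in SAP 4.3, and the physical-examination tabulation in Protocol 11.3.5.1, have no planned output in a study whose primary objective is long-term safety. The planned safety evidence is limited to TEAE tables, deaths and survival, and disposition. Two things would not be shown: laboratory, ECG or vital-sign changes that were not reported as adverse events, and the number of patients meeting the Protocol 6.5 numeric laboratory criteria.

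The size of the loss is a matter of scope (2 of 3 endpoints, 0 of 6 outputs). The documents give no basis for saying that a signal exists or has been missed. Physical and neurological examinations should not be described as dropped SAP endpoints, because 4.3 does not list them.

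The conclusion assumes that the visits before termination were carried out broadly as scheduled in Protocol Table 1, so that data exist to summarise. It does not depend on the number of patients dosed.

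**What to change.** Replace SAP 5.6.2 with a minimal set on SAFe, presented overall and by ADORE randomised group, and add the tables to SAP 9.3:

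1. Absolute values and change from baseline by visit for laboratory tests, QTcF and vital signs, following Protocol 11.3.5.4 to 11.3.5.6.
2. Baseline-to-worst counts (low, normal, high) for chemistry and haematology, with the worst value taken over scheduled and unscheduled measurements after the first extension dose.
3. Number and percentage of patients meeting each existing numeric laboratory criterion in Protocol 6.5, used exactly as written. State how creatinine clearance is derived. Where a criterion also needs symptoms, persistence or judgement, say that only the numeric part is counted.
4. Number and percentage of patients with abnormal physical or neurological examination findings. The neurological part goes beyond the tables in Protocol 11.3.5, but Protocol 8.2.1 uses that examination to look for peripheral nerve dysfunction.

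Name in SAP 6, with a reason, any item still dropped. Reconcile SAP 9.4 with section 14.3.2 in SAP 9.3, so that it is clear whether deaths and TEAEs are listed. If the database is already locked, produce the tables as supplementary output and label them so.

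The cost is a few standard tables from data the protocol already required. The main effort is harmonising ranges, because routine samples are analysed locally (note to Protocol Table 2). Expressing liver tests as multiples of the upper limit of normal reduces it.
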